For ALT/AST; subjects who screened prior to Protocol Version 11.0 were excluded if AST/ALT results were Grade 1 or higher at Screening. Subjects who screen with Protocol Version 11.0, AST/ALT is exclusionary if Screening results are  $1.5 \times$  ULN or if assessed as CS by the site PI.

\*\*Grade 1 or higher toxicity, see [Appendix C](#) and [Appendix D](#) for subjects who screened and enrolled prior to Protocol Version 11.0. Subjects who screen and enroll with Protocol Version 11.0, toxicity will be assessed with the NCI CTCAE, Version 5.0 – November 2017. Safety laboratory tests drawn on Day -1 or Screening if within 48 hours of planned dosing will serve as baseline values. Day -1 laboratory tests with a Grade 1 severity, other than those noted above, will not exclude subjects from participation.

\*\*\* All other abnormal laboratory values collected at Screening and on Day -1 will be exclusionary at the discretion of the PI.

22. Potassium, bicarbonate, or creatinine/eGFR\* results are Grade 1 or higher at either Screening or Day -1/Baseline visits.

\*For creatinine; subjects who screened prior to Protocol Version 11.0 were excluded if creatinine results were Grade 1 or higher. Subjects who screen with Protocol Version 11.0, creatinine is not an exclusionary criterion, instead subjects should have a calculated eGFR using Chronic Kidney Disease Epidemiology Collaboration Creatinine Equation (CKD-EPI) of  $\geq 90$  mL/min/1.73m^2 to be enrolled in the study.

23. Received an experimental agent (vaccine, drug, biologic, device, or medication) within 45 days or 5 half-lives (whichever is longer) before study product administration.\*

\*Prior participation at any time in noninvasive methodology trials in which no drugs were given is acceptable.

---

24. Is participating in or plans to participate in another clinical trial with an interventional agent that will be received during this trial.
25. Has donated more than 500 mL of blood or blood products\* within the month before Screening.  
\*Includes whole blood, red blood cells, platelets, plasma, or plasma derivatives.
26. Has a history of serologically-proven CHIKV exposure at any point, or positive anti-CHIKV antibodies (ie, positive IgM or IgG) at Screening.
27. Has received blood products within 120 days prior to Screening.

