#### **3.3. Study Definitions and Derived Variables**

##### **Baseline**

The baseline value will be the last value obtained prior to start of infusion of study product. In the case of ECG assessments, if triplicate measurements were performed at the last visit prior to study product administration, then baseline will be the mean value of the measurements from that visit. For example, if triplicate ECGs are performed on Day 1 prior to dosing, the baseline ECG value for the purpose of analysis would be the mean value of these measurements.

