## 6. GENERAL STATISTICAL CONSIDERATIONS

### 6.1. General Principles

Unless otherwise specified, continuous variables will be summarized by the following descriptive statistics: the number of participants with non-missing data included in the analysis (n), mean, standard deviation (SD), median, minimum value (min), and maximum value (max). Summary statistics for discrete data will include frequencies and proportions and may include confidence intervals (CIs) for the proportion. When 95% CIs are given for a proportion, exact (Clopper-Pearson) CIs will be used, unless otherwise specified.

All randomized participants will be included in summaries of participant demographics. The Safety Population will be used for summaries of safety endpoints, the PK Population will be used for summaries of PK endpoints, and the Immunogenicity Population or the Pharmacokinetics – Immunogenicity Subset Population will be used for summaries of immunogenicity endpoints. Denominators for clinical, clinical laboratory, VS, and ECG results at planned study time points will be the number of participants in the Safety Population with available results at the specified time point for that parameter. Denominators for the conceptual “Maximum Severity Post Baseline” time point for clinical, clinical laboratory, VS, and ECG results will be the number of participants with an observed result for the parameter obtained post-dose. Unless otherwise specified, denominators for all other safety endpoints will be the number of participants in the Safety Population. All tables will be annotated with the total population size relevant to that table/group, including any missing observations.

The sort order for listings is indicated in the implementation note for each listing shell. The sort order of treatment groups is given in [Section 3](#). The sort order of clinical laboratory tests, VS, and ECG parameters is described in [Section 9](#).

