## **6.5. Missing Data**

All attempts will be made to collect all data per protocol. No imputation will be performed for missing values.

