#### 14.3.5.4 Urinalysis Results

**Table 173: Laboratory Results by Severity, Time Point, and Treatment Group for Participants in the Safety Population Enrolled Prior to Protocol v11.0 – Any Urinalysis Parameter**

[Implementation Note: Repeat for the following treatment groups: All Participants, SAR440894 0.3 mg/kg, SAR440894 1 mg/kg, SAR440894 3 mg/kg, SAR440894 10 mg/kg, SAR440894 20 mg/kg, Placebo.]

The table will include the following time points: Baseline, Day 2, Day 3, Day 4, Day 7, Day 14, Day 28, Day 56, Day 84, Day 112, Final Visit (Day 150), Max Severity Post Baseline.]

Time Point	Treatment Group	Baseline Severity	Post-Baseline Severity					
			None		Mild / Grade 1		Moderate/ Grade 2	
			n	%	n	%	n	%
Day 2	All Participants (N=X)	None						
		Mild						
	SAR440894 0.3 mg/kg (N=X)	None						
		Mild						
	...	...						
		...						
	Placebo (N=X)	None						
		Mild						
...	...	...						
Max Severity Post Baseline	All Participants (N=X)	None						
		Mild						
	SAR440894 0.3 mg/kg (N=X)	None						
		Mild						
	...	...						
		...						

**Table 173: Laboratory Results by Severity, Time Point, and Treatment Group for Participants in the Safety Population Enrolled Prior to Protocol v11.0 – Any Urinalysis Parameter (continued)**

Time Point	Treatment Group	Baseline Severity	Post-Baseline Severity							
			None		Mild / Grade 1		Moderate/ Grade 2		Severe/ Grade 3	
			n	%	n	%	n	%	n	%
Placebo (N=X)	None									
		Mild								

Notes: The “Max Post Baseline” rows indicate the maximum severity experienced by each participant at any time point post baseline, including unscheduled assessments. N = Number of participants in the Safety Population enrolled prior to Protocol v11.0 with non-missing results at the given time point.

**Table 174: Laboratory Results by Severity, Time Point, and Treatment Group for Participants in the Safety Population Enrolled Under Protocol v11.0 – Any Urinalysis Parameter**

[Implementation Note: Repeat for the following treatment groups: All Participants, SAR440894 0.3 mg/kg, SAR440894 1 mg/kg, SAR440894 3 mg/kg, SAR440894 10 mg/kg, SAR440894 20 mg/kg, Placebo.

The table will include the following time points: Baseline, Day 2, Day 3, Day 4, Day 7, Day 14, Day 28, Day 56, Day 84, Day 112, Final Visit (Day 150), Max Severity Post Baseline.]

Time Point	Treatment Group	Baseline Severity	Post-Baseline Severity											
			None		Mild / Grade 1		Moderate/ Grade 2		Severe/ Grade 3		Life-threatening/ Grade 4		Death/ Grade 5	

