Time Point	Treatment Group	Baseline Severity	Post-Baseline Severity			
			Within Normal Range		Outside Normal Range	
			n	%	n	%
Notes: The “Max Post Baseline” rows indicate the maximum severity experienced by each participant at any time point post baseline, including unscheduled assessments. N = Number of participants in the Safety Population enrolled under Protocol v11.0 with non-missing results at the given time point. ONR = Outside of Normal Range.						

**Tables with Similar Format:****Table 193: Laboratory Results by Severity, Time Point, and Treatment Group for Participants in the Safety Population Enrolled Prior to Protocol v11.0 – Leukocyte Esterase**

[Implementation Note: This table will have similar format to Table 191.]

**Table 194: Laboratory Results by Severity, Time Point, and Treatment Group for Participants in the Safety Population Enrolled Under Protocol v11.0 – Leukocyte Esterase**

[Implementation Note: This table will have similar format to Table 192.]

**Table 195: Laboratory Summary Statistics by Time Point and Treatment Group for the Safety Population – Urine WBC (wbc/hpf)**

[Implementation Note: Repeat for the following treatment groups: SAR440894 0.3 mg/kg, SAR440894 1 mg/kg, SAR440894 3 mg/kg, SAR440894 10 mg/kg, SAR440894 20 mg/kg, Placebo.]

The table will include the following time points: Baseline, Day 2, Day 3, Day 4, Day 7, Day 14, Day 28, Day 56, Day 84, Day 112, Final Visit (Day 150).]

Time Point	Treatment Group	Value at Visit					Change from Baseline				
		n	Mean	SD	Median	Min, Max	n	Mean	SD	Median	Min, Max
Baseline	SAR440894 0.3 mg/kg (N = X)	x	xx.x	xx.x	xx.x	xx.x, xx.x	-	-	-	-	-
	...						-	-	-	-	-
	Placebo (N = X)						-	-	-	-	-
Day 2	SAR440894 0.3 mg/kg (N = X)						x	xx.x	xx.x	xx.x	xx.x, xx.x
	...										
	Placebo (N = X)										
...	...										

Notes: N = Number of participants in the Safety population. n = Number of participants with a non-missing lab value at the respective visit. For the change from baseline, n represents the number of participants with non-missing values at baseline and the respective visit. SD = Standard Deviation. Min = Minimum. Max = Maximum.

**Tables with Similar Format:****Table 196: Laboratory Summary Statistics by Time Point and Treatment Group for the Safety Population – Urine RBC (rbc/hpf)****Table 197: Laboratory Summary Statistics by Time Point and Treatment Group for the Safety Population – Urobilinogen (mg/dL)**

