[Implementation Note: Generate one table for each chemistry parameter. For calculated fields (Mean, SD, Median), decimal place should be the format in which the data were collected + 1 extra place. For Min, Max, decimal place should be in the same format in which the data were collected.]

[Repeat for each Chemistry Laboratory Parameter, number each table separately]

**Table 198: Clinically Significant Graded Urinalysis Results by Maximum Severity Post-Baseline, Parameter, and Treatment Group for Participants in the Safety Population Enrolled Prior to Protocol v11.0**

[Implementation Note: Repeat for the following treatment groups: All Participants, SAR440894 0.3 mg/kg, SAR440894 1 mg/kg, SAR440894 3 mg/kg, SAR440894 10 mg/kg, SAR440894 20 mg/kg, and Placebo.

The table will include the following parameters: Urine Protein, Urine Glucose, Bilirubin, Nitrite, Occult Blood, Urine WBC, Urine RBC, and Urobilinogen.]

Parameter	Treatment Group	N	Mild / Grade 1		Moderate/ Grade 2		Severe/ Grade 3	
			n	%	n	%	n	%
Urine Protein	All Participants	x	x	xx	x	xx	x	xx
	SAR440894 0.3 mg/kg							
	...							
	Placebo							
Urine Glucose	All Participants							
	SAR440894 0.3 mg/kg							
	...							
	Placebo							
Bilirubin	All Participants							
	SAR440894 0.3 mg/kg							
	...							
	Placebo							
...	...							

Notes: Participants are counted once per maximum severity among all clinically significant labs experienced at any time point post baseline, including unscheduled assessments. N = Number of participants in the Safety Population enrolled prior to Protocol v11.0 with available results post-baseline.

**Table 199: Clinically Significant Graded Urinalysis Results by Maximum Severity Post-Baseline, Parameter, and Treatment Group for Participants in the Safety Population Enrolled Under Protocol v11.0**

[Implementation Note: Repeat for the following treatment groups: All Participants, SAR440894 0.3 mg/kg, SAR440894 1 mg/kg, SAR440894 3 mg/kg, SAR440894 10 mg/kg, SAR440894 20 mg/kg, and Placebo.]

The table will include the following parameters: Urine Protein, Urine Glucose, Bilirubin, Nitrite, Occult Blood, Urine WBC, Urine RBC, and Urobilinogen.]

Parameter	Treatment Group	N	Mild / Grade 1		Moderate/ Grade 2		Severe/ Grade 3		Life-threatening/ Grade 4		Death/ Grade 5	
			n	%	n	%	n	%	n	%	n	%
Urine Protein	All Participants	x	x	xx	x	xx	x	xx	x	xx	x	xx
	SAR440894 0.3 mg/kg											
	...											
	Placebo											
Urine Glucose	All Participants											

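### Urine RBC and WBC percentages are taken only among participants whose dipstick triggered microscopy, and new-onset cases without a pre-dose count fall out of change from baseline

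*SAP*

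**What the plan says.** **When a count exists.** SAP Tables 5 and 6 grade urine RBC and urine WBC as microscopy counts (rbc/hpf, wbc/hpf). Microscopy is a reflex test after an abnormal dipstick: Protocol 6.2, 6.3 and 6.4.1, the note in Protocol Table 7-1, Appendix A footnote 8, SAP 4.5.1 and SAP Table 2 footnote 8. SAP 4.5.1 adds that microscopy results replace the dipstick result once microscopy is done. It does not say how urine RBC or WBC is classified when microscopy was not triggered.

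**Denominators.** Under SAP 6.1 the by-visit denominator "will be the number of participants in the Safety Population with available results at the specified time point for that parameter". For maximum severity post baseline it "will be the number of participants with an observed result for the parameter obtained post-dose". The shells agree. The note to Table 173, the format for Tables 185 and 187, reads "N = Number of participants in the Safety Population enrolled prior to Protocol v11.0 with non-missing results at the given time point", and Tables 186 and 188 follow the matching Table 174. The note to Table 198 reads "N = Number of participants in the Safety Population enrolled prior to Protocol v11.0 with available results post-baseline", and Table 199 follows the same pattern for Protocol v11.0.

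**Baseline and missing data.** SAP 3.3: "The baseline value will be the last value obtained prior to start of infusion of study product". The note to Table 195, whose format Table 196 shares: "For the change from baseline, n represents the number of participants with non-missing values at baseline and the respective visit". SAP 6.5: "No imputation will be performed for missing values".

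**The concern.** Whether a participant has a count depends on the dipstick, so it depends on the outcome being summarised. Someone with a clean dipstick was tested and found unremarkable, but leaves the denominator as if untested. One participant with an elevated count is then shown as 1 of *m*, where *m* is the number in that group who happened to have microscopy at that visit. The percentage moves with unrelated dipstick abnormalities in the same group, so dose groups cannot be compared with each other or with placebo.

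The baseline has the same problem. A participant with clean dipsticks before dosing and an elevated count afterwards has no baseline count. That person cannot contribute to change from baseline and has no stated row in the shift tables, whose shells stratify by a baseline severity of None or Mild.

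Clinically significant laboratory changes are part of the primary endpoint (SAP 3.2.1). Protocol 2.1 names the kidney as the target organ in mice, and Protocol 2.3.1 reports a mild increase in hematuria/hemoglobinuria in male monkeys at 45 mg/kg. Urine red cells are thus a display that readers will look at closely.

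**Working it through.** The plan states no figure for this point, so there is nothing to reproduce. Inputs from the documents: 6 participants per dose group and 10 pooled placebo (SAP Table 1), and 10 scheduled post-dose urine visits (Days 2, 3, 4, 7, 14, 28, 56, 84, 112 and 150; Protocol Appendix A). Assumptions: a trigger probability *p* per sample of 5%, 10% or 20%; participants independent; and the case itself always triggered.

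**1. Direction.** With *x* cases, *m* participants with microscopy and *n* tested by dipstick, the plan shows *x/m* instead of *x/n*. Since *m* ≤ *n*, the shown value is never lower, and the two are equal only if everyone triggers. For one case in 6: 1/1 = 100%, 1/2 = 50% or 1/3 = 33%, against 1/6 = 17%.

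**2. Average size for one case.** Let K ~ Bin(n−1, q) be the number of other participants with a count. Then E[1/(1+K)] = [1 − (1−q)^n]/(nq). By visit, q = p. For n = 6 and p = 0.05: (1 − 0.95^6)/(6 × 0.05) = 0.2649/0.30 = 0.883.

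For rows pooled over 10 visits (maximum severity, Tables 198/199), q is the chance of at least one trigger. With independent visits q = 1 − (1−p)^10 = 0.401, 0.651, 0.893. With within-person correlation ρ under a beta-binomial model, q = 0.197, 0.359, 0.601 at ρ = 0.3 and 0.138, 0.260, 0.462 at ρ = 0.5. If triggers always recur in the same people, q = p.

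| One case in | Display | p = 5% | p = 10% | p = 20% |
|---|---|---|---|---|
| 6 (17%) | by visit | 88% | 78% | 61% |
| 6 (17%) | pooled, independent | 40% | 26% | 19% |
| 6 (17%) | pooled, ρ = 0.3 | 62% | 43% | 28% |
| 6 (17%) | pooled, ρ = 0.5 | 71% | 54% | 35% |
| 6 (17%) | pooled, always the same people | 88% | 78% | 61% |
| 10 (10%) | by visit | 80% | 65% | 45% |
| 10 (10%) | pooled, independent | 25% | 15% | 11% |

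The tables are also split by protocol version (SAP 6.7). If a dose group happened to split 3 and 3, one case in 3 (33%) would be shown by visit as 95%, 90%, 81%.

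**3. Baseline counts.** With independent samples, the share of new-onset cases with no baseline count is 1 − p = 95%, 90%, 80% if only Day -1 can supply it. If a Screening count may stand in, as SAP 3.3 read literally allows, the share is (1−p)^2 = 90%, 81%, 64%.

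The expected number of 6 participants contributing to change from baseline at a visit is then:

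- Day -1 only: 6p² = 0.015, 0.06, 0.24. The cell is empty with probability (1−p²)^6 = 99%, 94%, 78%.
- Screening or Day -1: 6p[1 − (1−p)²] = 0.03, 0.11, 0.43. The cell is empty 97%, 89%, 64% of the time.
- Fully persistent triggers: 6p = 0.3, 0.6, 1.2. The cell is empty with probability (1−p)^6 = 74%, 53%, 26%.

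**The case against.** **The dipstick may be meant to stand.** Because SAP 4.5.1 lets microscopy replace the dipstick, one can argue that the dipstick result applies when nothing replaces it, which would place an untriggered sample under None. That is a sensible intention, but the text does not say it. Occult blood and leukocyte esterase are separate SAP parameters, which weighs against carrying them over into RBC and WBC counts, and SAP 6.1 and 6.5 read literally point the other way.

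**Other displays cover the signal.** This largely stands. Dipstick occult blood (Tables 183/184) and leukocyte esterase (Tables 193/194) are not conditional on microscopy. The any-urinalysis tables (173/174) also have a wider base, and Tables 68/69 and Listing 18 show individual results. Tables 198/199 have no baseline stratum and still count a new case. Table 195 prints n beside N, and SAP 6.1 asks for the total population size on every table. A reader who infers that hematuria would be hidden goes too far. None of these displays, however, corrects the RBC and WBC percentages. For participants enrolled before v11.0, the microscopic red cell count is also the only blood-in-urine measure with grading limits in SAP Tables 5 and 6.

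**A baseline conflict between the documents.** A reader might infer one from the note to exclusion criterion 21 in Protocol 5.1.2: "Safety laboratory tests drawn on Day -1 or Screening if within 48 hours of planned dosing will serve as baseline values". The documents do not support this. The protocol's analysis definition in 10.5.1.2 takes the measurement closest to but before dosing, and SAP 3.3 agrees with it.

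**The size is assumed.** True. The documents give neither a trigger rate nor a within-person correlation. Nor are 6 and 10 upper limits on group size: Protocol 5.2.2 allows replacement after dosing, and the Safety Population keeps everyone dosed. They are the planned sizes.

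**Conclusion.** The point holds for urine RBC and urine WBC, 2 of the 10 SAP urinalysis parameters. It rests on a stated denominator rule combined with reflex testing, not on silence alone. The direction needs no assumption about trigger rates: unless everyone triggers, the shown percentage of cases exceeds the percentage among all tested. By visit the distortion is likely to be large when triggers are uncommon (88%, 78%, 61% in place of 17% at the assumed rates). In pooled rows it runs from slight (19%) to as large as by visit, depending on how far triggers recur in the same people. Change from baseline in Tables 195-196 would rest on few or no participants and would leave out new-onset cases with no pre-dose count.

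The analysis is descriptive and the signal remains visible elsewhere, so no trial conclusion is overturned. It still merits correction before unblinding, because choosing a denominator afterwards would be a post-hoc decision on a renal safety display.

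**What to change.** Before unblinding:

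1. Add a rule to SAP 4.5.1 and 6.1, for example: *For urine RBC and urine WBC, a sample whose dipstick did not trigger microscopy is classified as None, at baseline and post-dose. This is a classification rule, not imputation. The baseline category comes from the last pre-infusion urine sample (SAP 3.3). The denominator is participants with either a microscopy result or an untriggered dipstick at that time point, or at any post-dose time for maximum-severity and clinically significant rows. Triggered samples without a microscopy result are excluded and their number is shown.*
2. Apply it to Tables 185-188 and 198/199.
3. Drop Tables 195-196 and Figure 45, or label them 'microscopy-triggered samples only'.
4. Reconcile the three descriptions of the trigger, since they decide who has a count: red cells, white cells or protein (Protocol 6.2, 6.3, 6.4.1); any abnormal dipstick value (note in Protocol Table 7-1, SAP 4.5.1); and a dipstick read for protein, glucose or blood (footnote 8 of Protocol Appendix A and of SAP Table 2).

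The cost is SAP wording, table programming and one reconciliation between the documents. No new sample, assay or visit is needed.

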### 6.2. Timing of Analyses

A final CSR will be prepared after all safety, PK, and immunogenicity data are available following database lock.

Safety data will be reviewed in real time by the site PI(s) to evaluate whether cohort dose escalation halting rules or study halting criteria have been met, and findings will be shared with the DMID MM and Evotec medical officer. Blinded safety and clinical laboratory data up to the Day 14 visit will be evaluated by the SRC after each cohort. Interim cumulative safety data to determine escalation to higher dose will be presented to the SRC after completion of Cohort 1. After each additional cohort, the SRC will review blinded safety and clinical laboratory data through Day 14 via study web reports to determine escalation to a higher dose.

The SMC may be convened ad hoc at the recommendation of the SRC in response to a safety issue. An end of study summary of summary of final cumulative safety data will be provided for the SMC to review will be provided for the SMC to review once final safety data are once final safety data are available after database lock.

### 6.3. Analysis Populations

All analysis populations to be used in the final analysis are described in this section. A tabular listing of all randomized and enrolled participants excluded from an analysis population (Safety Population, PK Population, Immunogenicity Population, or Pharmacokinetics – Immunogenicity Subset Population) will be included in the CSR ([Listing 5](#)). Reasons for exclusion from analysis populations will be summarized in [Table 8](#).

### **6.3.1. Safety Population**

The Safety Population will include all participants who receive any amount of study product.

